5.5. Compliance Statement

This clinical trial will be conducted in accordance with standards of Good Clinical Practice (GCP) as defined by the International Conference on Harmonisation (ICH) and all applicable federal and local regulations.

6. OBJECTIVES

6.1. Safety Objective

The primary objective is:

- To evaluate the long term safety of repeat doses of ALD403 administered intravenously (IV) in chronic migraine patients

6.2. Immunogenicity and Patient Reported Outcomes

The secondary objective is:

- To evaluate the pharmacokinetics (PK) and immunogenicity of repeat doses of ALD403 administered IV to patients with chronic migraine.
- To further evaluate the impact of ALD403 on various patient reported outcomes.

7. TRIAL DESIGN

7.1. Clinical Trial Endpoints

7.1.1. Safety Endpoints

- Adverse events (AEs) and serious adverse events (SAEs)
- Clinical laboratory assessments
- Vital Signs
- ECGs
- Columbia-Suicide Severity Rating Scale (C-SSRS)

7.1.2. Patient Reported Outcomes:

- Patient Global Impression of Change (PGIC)
- Short-Form Health Survey (SF-36)
- Health-Related Quality of Life (EQ-5D-5L)
- Headache Impact Test (HIT-6)
- Most Bothersome Symptom (MBS)
- The Migraine Disability Assessment (MIDAS)

7.1.3. PK and Immunogenicity Endpoints:

- Free ALD403 plasma concentrations
- Development of specific anti-ALD403 antibodies
- Characterization of specific anti-ALD403 antibodies for neutralizing activity

7.2. Clinical Trial Design

This is an open label trial of intravenous (IV) infusions of ALD403 in patients with chronic migraine. The trial will include two treatment phases. The primary treatment phase will include 4 infusions of ALD403 12 weeks apart. The secondary treatment phase will include up to 4 additional infusions of ALD403 12 weeks apart following the primary treatment phase.

Subjects who provide informed consent will be evaluated for eligibility based upon the inclusion and exclusion criteria. In the primary treatment phase, visits will occur on Day 0, Weeks 2, 4, 8, 12, 24, and 36 and subjects will receive 4 IV infusions of ALD403 on Days 0, Weeks 12, 24, and 36.

Subjects who receive all 4 infusions of ALD403 in the primary treatment phase may enter the secondary treatment phase. In the secondary treatment phase, subjects will receive up to 4 additional infusions for a total of 8 infusions. Visits and ALD403 IV infusions will occur on Weeks 48, 60, 72, and 84. Subjects will be followed for 20 weeks until Week 104 for a total study duration of approximately 106 weeks, including the screening period.

Subjects who don't receive all 4 infusions of ALD403 in the primary treatment phase or don't consent for participation in the secondary treatment phase will be followed at Week 48 and Week 56, at which point they will have their End of Trial visit.

Approximately 120 subjects will be enrolled and treated. Study specific assessments will be conducted according to the Schedule of Events presented in [Section 2](#).

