Investigational Product, Dose and Schedule	Eight intravenous infusions of 300mg ALD403 will be given 12 weeks apart. Infusions will occur on Day 0, Week 12 (Day 84 +/- 3 days); Week 24 (Day 168 +/- 3 days); Week 36 (Day 252 +/- 3 days); Week 48 (Day 336 -7/+14 days); Week 60 (Day 420 +/- 7 days); Week 72 (Day 504 +/- 7 days); and Week 84 (Day 588 +/- 7 days).
Duration of Treatment	Up to 8 IV infusions of ALD403 will be given approximately 12 weeks apart over an 84 week period.
Duration of Clinical Trial Participation	The trial participation period is approximately 106 weeks which includes: 
• 2-week screening period,• 48-week primary treatment administration period,• 36-week secondary treatment administration period• 20-week follow-up period.
Clinical Trial Endpoints	
Safety Endpoints
 
• Adverse events (AEs) and serious adverse events (SAEs)• Clinical laboratory assessments• Vital Signs• Electrocardiograms (ECGs)• Columbia-Suicide Severity Rating Scale (C-SSRS) 
Patient Reported Outcomes
 
• Patient Global Impression of Change (PGIC)• Short-Form Health Survey (SF-36)• Health-Related Quality of Life (EQ-5D-5L)• Headache Impact Test (HIT-6)• Most Bothersome Symptom (MBS)• Migraine Disability Assessment (MIDAS) 
PK and Immunogenicity Endpoints
 
• Free ALD403 plasma concentrations• Development of specific anti-ALD403 antibodies• Characterization of specific anti-ALD403 antibodies for neutralizing activity
Concomitant Medications	
• Subjects on stable medication for headache prophylaxis for 3 months prior to screening will be permitted to continue use during the study, provided there are no alterations to their regimen, except as allowed per Investigator discretion. After Week 48, changes to migraine prophylactic treatment are

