5.3.3. Dose Justification

A dose of 300mg ALD403 administered by IV infusion every 12 weeks has shown efficacy in the treatment of CM and is the maximum anticipated dose and schedule. No dose limiting, treatment related adverse effects have been observed following ALD403 administration up to 1000mg. ALD403 single dose levels up to 1000mg have generally been well tolerated.

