3.3.6 Clinical Trial Treatment

Total volume infused, number of infusions and reason for dose interruption will be listed as well as summarized in a table.

3.4 *Efficacy Analyses*

The secondary endpoints of patient reported outcomes (PROs) will be summarized with descriptive statistics by time point. These summary measures will be based upon the observed results and where appropriate the change from baseline results. The denominator for percentages will be the total number of PROs collected at each visit since not all subjects will complete PROs at all visits.

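### The Week 48 and Week 60 windows conflict with the stated 12-week interval: after a Week 48 infusion on Days 344-350, no permitted Week 60 date is 84 days later, and the permitted gap can be as short as 63 days

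*Protocol*

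**What the plan says.** **Interval.** Protocol 7.2 says of the second phase: "The secondary treatment phase will include up to 4 additional infusions of ALD403 12 weeks apart following the primary treatment phase". The dose row of the synopsis covers the whole course: "Eight intravenous infusions of 300mg ALD403 will be given 12 weeks apart". The duration row is softer: "Up to 8 IV infusions of ALD403 will be given approximately 12 weeks apart over an 84 week period". SAP 1.2 also spaces the infusions at 12 weeks. Protocol 5.3.3 says that 300 mg every 12 weeks "is the maximum anticipated dose and schedule".

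**Windows.** The synopsis gives "Week 48 (Day 336 -7/+14 days" and "Week 60 (Day 420 +/- 7 days". Protocol Section 2 and SAP Table 1 give the same windows. The day numbers run from Day 0. SAP 2.3 likewise counts trial day from a single treatment date. Neither document ties the Week 60 visit to the actual Week 48 date or states a minimum gap between infusions.

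**Reporting.** SAP 3.3.6 describes the exposure output: "Total volume infused, number of infusions and reason for dose interruption will be listed as well as summarized in a table". Time between infusions is not among the items. The Schedule of Events has PK and antibody samples at Weeks 48 and 72 but not at Week 60. AE review, vital signs, ECG and laboratory tests are scheduled at Week 60.

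**The concern.** Week 48 is the only infusion visit with a 14-day allowance on the late side, and nothing later in the schedule absorbs it. A subject infused late at Week 48, within the window, reaches a Week 60 window that closes before 12 weeks have passed. The site must then either miss that window or infuse at less than the stated interval. Protocol 14.6 requires the protocol to be followed exactly, so the site cannot satisfy both statements.

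The primary objective is the long-term safety of repeat doses, and 5.3.3 describes the 12-week regimen as the upper end of what is anticipated. If some second-year infusions come at a clearly shorter interval because the windows require it, the report should say so. As specified, the SAP's exposure table would not separate them. The SAP's Week 60 analysis window (Days 379-462) groups results by trial day, whatever the time since the last infusion.

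**Working it through.** **Inputs.** Target days and windows come from the synopsis dose row and Protocol Section 2. The stated interval is 12 weeks = 84 days.

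**Step 1: the plan's own figure.** Week 60 target minus Week 48 target = 420 - 336 = 84 days. The stated interval is reproduced on target days.

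**Step 2: windows in days.**
- Week 48: 336 - 7 = 329 to 336 + 14 = 350, which is 22 permitted days.
- Week 60: 420 - 7 = 413 to 420 + 7 = 427.

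**Step 3: permitted gaps for every consecutive pair.** Shortest gap = earliest next day - latest previous day. Longest gap = latest next day - earliest previous day. The last column lists first-infusion days from which even the latest permitted next day is under 84 days away.

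| Pair | First infusion (days) | Next infusion (days) | Shortest gap | Longest gap | 84 days unreachable from |
|---|---|---|---|---|---|
| Day 0 to Week 12 | 0 | 81-87 | 81 | 87 | none |
| Week 12 to 24 | 81-87 | 165-171 | 78 | 90 | none |
| Week 24 to 36 | 165-171 | 249-255 | 78 | 90 | none |
| Week 36 to 48 | 249-255 | 329-350 | 74 | 101 | none |
| Week 48 to 60 | 329-350 | 413-427 | 63 | 98 | Days 344-350 |
| Week 60 to 72 | 413-427 | 497-511 | 70 | 98 | none |
| Week 72 to 84 | 497-511 | 581-595 | 70 | 98 | none |

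**Step 4: where the Week 48 window fails.**
- Day 343: Week 60 falls 413 - 343 = 70 to 427 - 343 = 84 days later. Twelve weeks is just reachable.
- Day 344: 413 - 344 = 69 to 427 - 344 = 83 days. Twelve weeks is not reachable.
- Day 350: 413 - 350 = 63 to 427 - 350 = 77 days, or 9 to 11 weeks.

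Days 344-350 are 7 of the 22 permitted days. The largest shortfall is 84 - 63 = 21 days. In the primary phase, Day 0 to Week 36, it is 84 - 78 = 6 days.

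**Step 5: a threshold that isolates the problem.** A permitted gap under 70 days needs 413 - x < 70, so x > 343. Within the windows, such a gap can follow only a Week 48 infusion on Days 344-350, and no other pair permits one.

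**The case against.** The strongest reply is that 12 weeks is a nominal interval and the windows are its tolerance. The target days are exactly 84 days apart, the dose row lists the windows immediately after stating the interval, and the duration row says the interval is approximate. This stands for ordinary scheduling variation. Every pair in the table permits some gap under 84 days, so a reader who infers that any gap below 84 days breaches the plan goes too far. An 84-day cut-off would also sweep in infusions given only a day or so early. The reply does not cover Days 344-350. There the windows do more than allow a shorter gap: they rule out the stated one. That happens at no other pair.

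Three further readings are tempting and not supported.

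- **A safety hazard or materially higher exposure.** The documents give no half-life, so the effect on drug levels cannot be derived from them. Protocol 5.3.3 also reports that single doses up to 1000 mg were generally well tolerated. That does not establish the safety of a shorter repeat interval, but nothing in the documents shows harm.
- **That about a third of subjects are affected.** Seven of 22 is a count of permitted days. Visits aim at a target day, and the documents do not show how many, if any, will fall on Days 344-350.
- **That nothing planned could reveal it.** Clinical safety assessments take place at Week 60, PK and antibody samples follow at Week 72, and SAP 3.5 refers to a population PK analysis and a separate PK plan that may use actual dose times. What can be said is that the SAP's exposure summary omits the interval, and that the level just before the Week 60 infusion is not sampled. Week 84 has no PK sample either, so the missing sample reflects sparse sampling generally and is not itself an error.

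**Conclusion.** The documents conflict at one place. For a Week 48 infusion on Days 344-350, the stated 12-week interval and the Week 60 window cannot both be met. The permitted Week 48 to Week 60 gap runs from 63 to 98 days overall, and from 63 to 77 days after Day 350. The next shortest permitted gap anywhere in the schedule is 70 days. For Week 48 on Days 329-343 an 84-day gap remains available.

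This rests only on the stated windows, on counting days from Day 0, and on the absence of any rule that re-anchors Week 60 or sets a minimum gap. It needs no assumption about visit patterns or pharmacokinetics. The conclusion is limited to an inconsistency in the schedule and an exposure summary that would not display its effect. It does not show that any safety result would change.

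**What to change.** 1. Reconcile the interval statements (synopsis, Protocol 5.3.3 and 7.2, SAP 1.2) with the Week 48 and Week 60 windows (synopsis, Protocol Section 2, SAP Table 1). The sponsor decides whether the interval wording, the windows or the day from which they are counted should change.
2. In SAP 3.3.6, add actual days since the previous infusion (median, minimum, maximum) for each infusion after the first.
3. Identify Week 60 infusions that follow a Week 48 infusion on Days 344-350, and any infusion given after a gap under 70 days, and list the AEs that follow them.

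The cost is protocol and SAP wording, one row in the exposure table and a short listing. No new data are needed: SAP 3.6.2.1 already defines infusion-related events by time from dosing, which requires the date of each infusion.

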13. STATISTICAL CONSIDERATIONS

13.1. Sample Size

The planned sample size for the study is 120 treated subjects. It is assumed that over 75% of these subjects will complete the primary treatment phase resulting in at least 90 subjects with one year of safety data collection.

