13.4.2. Efficacy Analyses

The Secondary endpoints will be summarized with descriptive statistics by time point. These summary measures will be based upon the observed results and where appropriate the change from baseline results. Testing of these change from baseline results for the SF-36, MIDAS and HIT-6 will be performed at Weeks 12, 24, 36, 48, 60, 72, 84 and 104. For SF-36 tests will be performed for the change in the Mental Component and Physical Component scores and for the HIT-6 and MIDAS tests will be performed based upon the change in total score. The tests will be a t-test.

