3.4.4 Patient Global Impression of Change (PGIC)

The change in disease status since the start of the study will be summarized for PGIC using the Safety Population at each scheduled visit.

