3.4.5 Headache Impact Test (HIT-6)

The actual score and change from baseline in the total score will be summarized using the Safety Population at each scheduled visit. A shift from baseline to each scheduled visit will be tabulated. Testing of the change from baseline results will be performed at Weeks 12, 24, 36, 48, 60, 72, 84 and Week 104. T-tests will be performed based upon the change in total score.

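### Patient-reported results after Week 48 come increasingly from subjects who chose to continue, yet are reported with Weeks 12–48 under one population label, so lasting benefit cannot be told from selection

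*Protocol*

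**What the plan says.** **Who can continue.** Protocol 7.2: "Subjects who receive all 4 infusions of ALD403 in the primary treatment phase may enter the secondary treatment phase". Those who did not receive all four infusions, or who "don't consent for participation in the secondary treatment phase will be followed at Week 48 and Week 56, at which point they will have their" closing assessment, leave the trial then. SAP 1.2 says the same.

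**What is analysed.** For HIT-6, SAP 3.4.5 states: "Testing of the change from baseline results will be performed at Weeks 12, 24, 36, 48, 60, 72, 84 and Week 104". SAP 3.4.2 and 3.4.6 repeat this for the SF-36 component scores and MIDAS, and Protocol 13.4.2 gives the same list ("MIDAS and HIT-6 will be performed at Weeks 12, 24, 36, 48, 60, 72, 84 and 104"). The change in PGIC "will be summarized for PGIC using the Safety Population at each scheduled visit" (SAP 3.4.4).

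**On whom.** SAP 2.1 defines only a Safety and a PK population. SAP 2.6.1 uses observed data. SAP 3.4 adds: "The denominator for percentages will be the total number of PROs collected at each visit since not all subjects will complete PROs at all visits".

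**How results are assigned to visits.** SAP 2.3 assigns them by actual date. Table 2 gives Week 60 as Days 379–462 and has no row for Week 56, although the Schedule of Events places the Week 56 End of Trial visit at Day 392 ± 7.

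**The concern.** Entry to the secondary phase is selected twice: by having received every primary infusion, and by choosing to go on with an open-label drug after about a year's experience of it. If subjects who improved more are likelier to continue, mean improvement and the share of favourable PGIC ratings rise when the others leave, even if no individual changes. Selection could equally hide a decline among those who stay.

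Four of the eight tested visits (Weeks 60, 72, 84 and 104) lie after the decision to continue. They carry the same tests and population label as the earlier four, which invites a reader to follow the means across Week 48 as evidence of sustained or growing benefit. The plan has no summary of continuers' own Weeks 12–48 results, no comparison of continuers with non-continuers, and no missing-data sensitivity analysis for these outcomes.

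**Working it through.** **1. The plan's own figure.** Protocol 13.1 sets the size: "The planned sample size for the study is 120 treated subjects". On retention the same section says: "It is assumed that over 75% of these subjects will complete the primary treatment phase resulting in at least 90 subjects with one year of" follow-up for safety. The product is 120 × 0.75 = 90, which reproduces. The documents give no number entering the secondary phase, no SD of change and no relation between response and continuing. Those inputs below are assumptions.

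**2. Who is in each analysed visit.** The Week 56 visit spans Days 392 − 7 = 385 to 392 + 7 = 399, wholly inside Days 379–462. A non-continuer's Week 56 questionnaire is therefore analysed as Week 60.

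| Analysed visit | SF-36, HIT-6, MIDAS, PGIC | EQ-5D-5L, MBS |
|---|---|---|
| Weeks 12–48 | All treated subjects still observed | Same |
| Week 60 | Continuers at Week 60 plus non-continuers at Week 56 | Essentially non-continuers only |
| Weeks 72–104 | Continuers only | Not scheduled |

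The EQ-5D-5L and MBS column follows from the Schedule of Events: after Week 48 these two are collected only at a Week 56 End of Trial visit. Within Week 60, continuers are 60 − 48 = 12 weeks past an infusion. A non-continuer who had the Week 36 infusion is 56 − 36 = 20 weeks past it.

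**3. Size of the shift with no true change after Week 48.** Let q be the share continuing and D the mean improvement of continuers minus that of the others. The all-subject mean is the continuers' mean minus (1 − q)D, so the apparent step when the others leave is (1 − q) × D. At q = 0.75 and D = 0.5 SD this is 0.25 × 0.5 = 0.125 SD.

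Alternatively, let continuing depend on a normal variable with correlation r to improvement. The step in SD of change is r × φ(z)/q, where φ is the standard normal density and z cuts off the top share q. The factor φ(z)/q is 0.424 at q = 0.75, 0.545 at two-thirds and 0.798 at one-half.

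| Share continuing (of 120) | r = 0 | r = 0.2 | r = 0.4 | r = 0.6 |
|---|---|---|---|---|
| 75% (90) | 0 | 0.08 | 0.17 | 0.25 |
| Two-thirds (80) | 0 | 0.11 | 0.22 | 0.33 |
| One-half (60) | 0 | 0.16 | 0.32 | 0.48 |

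The 75% row equals the planning minimum of 90 completers with every one continuing. Two-thirds is 80/90 = 89% of them, and one-half is 60/90 = 67%.

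**4. What the reader of the output would see.** Take q = 0.75, r = 0.6 and an assumed constant mean improvement of 0.80 SD. Weeks 12–48 show 0.80. If all non-continuers attend Week 56, Week 60 also shows 0.80. Weeks 72–104 show 0.80 + 0.25 = 1.05. Restricted to continuers, every visit shows 1.05 and the step disappears. On HIT-6, with an assumed SD of change of 5–9 points, the same step is 1.3–2.3 points (0.6–1.1 at r = 0.3).

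**The case against.** The strongest reply is that these are secondary, mostly descriptive outcomes in an uncontrolled safety study. Each t-test is a separate change from baseline, and no trend or durability test is planned. SAP 3.1 reports n, SAP 3.3.1 tabulates attendance and reasons for discontinuation, and SAP 3.3.6 tabulates the number of infusions, so the fall in numbers will be visible. An interim analysis after the primary phase may already supply much of an all-treated summary to Week 48. Results conditional on continuing are legitimate if described that way.

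Most of this stands and limits the point. But the tables show that subjects left, not whether those who left had responded less, and nothing planned describes the later results as conditional.

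Several stronger readings are tempting but unsupported:
- *Everything from Week 60 on is continuers only.* True of the visit schedule, not of the analysis, because Week 56 data fall into Week 60.
- *Weeks 12–48 represent the whole cohort.* They already lose early withdrawals, so the real step could be smaller than illustrated.
- *The stated objective cannot be answered.* Protocol 6.2 asks only about the impact of ALD403 on these outcomes. It attaches repeat doses to PK and immunogenicity, and it does not mention change over time.
- *Selection alone would make the later tests significant.* Those tests compare change with zero, not later visits with Week 48, so the size of the step does not settle them.
- *Benefit will be overstated.* The documents fix neither the direction nor the size of the link between response and continuing.

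**Conclusion.** The point holds as a gap in analysis and labelling. As planned, a reading of sustained or growing benefit across Week 48 cannot be separated from a change in who is measured, and the analysed Week 60 mixes two groups at different times since infusion. The window overlap and the change in composition follow directly from the documents.

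The size does not. The range of 0.08–0.48 SD rests on assumed correlations of 0.2–0.6, assumed continuation of 75% down to one-half, and no true change after Week 48. It is zero if continuing is unrelated to response. Permitted changes in migraine prophylaxis after Week 48 (Protocol 9.3) are a second difference between the two halves of the series. The primary safety objective is not affected. The change is worth making because it is cheap.

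**What to change.** 1. **SAP Table 2:** add a Week 56 End of Trial window for subjects not entering the secondary phase, and restrict Week 60 to secondary-phase subjects.
2. **SAP 3.4:** keep the all-treated summaries and tests through Week 48. Add the same summaries and tests for subjects who received the Week 48 infusion, with n at each visit: baseline to Week 104 for SF-36, HIT-6 and MIDAS; Week 4 to Week 104 for PGIC; and to Week 48 only for EQ-5D-5L and MBS.
3. **One extra table:** Week 48 change in each outcome, and PGIC, for continuers versus non-continuers. All six instruments are scheduled for everyone at Week 48, before any infusion that day.
4. **Labelling:** title the Weeks 60–104 results as secondary-phase subjects. State that they are conditional on continuing, and that further dropout and permitted prophylaxis changes occur after Week 48.

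This needs SAP wording and repeated tables on data already scheduled, with no new collection. The cost is more output and possibly a less favourable reading of the later visits. It does not remove the effect of dropout after Week 48, which is why n must be shown at each visit.
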